Faba beans are a rich source of protein, vitamins, minerals and dietary fibre, and are low in fat. They are vegan, genetically modified organism (GMO) free and free of common allergens. Faba bean has a well-balanced amino acid profile, similar to that of the pea and soy (see Table 1) (16). Clinical studies have shown that regular consumption of pulses (including faba beans) can reduce blood levels of total cholesterol and low-density lipoprotein (LDL), and therefore may reduce the risk of CVD. One of the key benefits of FPs over many other plant-based protein powders, including pea protein, is that it has a less grainy (creamier) texture and is more palatable. Overall, there is very little known about the basic digestion of FP in terms of the postprandial amino acid profile and its effect on metabolism after ingestion. This information is fundamental to understand before embarking on longer term human studies. To the best of our knowledge, no other study has examined the specific bioavailability, digestibility, and metabolism of FP compared to WP.

AIM

The aim of this study is to assess the acute effect of FP vs WP, with and without a glucose load, on satiety hormones, postprandial amino acid bioavailability, glucose, insulin and a range of metabolomic markers in circulating blood in healthy volunteers.

MAIN RESEARCH QUESTIONS AND HYPOTHESES BEING ADDRESSED

Question 1 – What effect does FP have on glucagon-like peptide-1 (GLP-1), other satiety hormones, amino acid availability, glucose, insulin and a range of metabolomic markers compared to the same dose of WP in healthy adults?

Hypothesis 1 – A beverage containing FP protein will have a similar stimulatory effect on GLP-1 and satiety hormone secretion but will have lower amino acid availability compared to WP.

Question 2 – What effect does FP together with a glucose load have on GLP-1 and other satiety hormones, amino acid availability, postprandial glycaemic, and insulinaemic response and a range of

metabolomic markers compared to the same dose of WP together with a glucose load in healthy adults?

Hypothesis 2 – A beverage containing FP and glucose will attenuate the postprandial glycaemic response to a greater extent than a beverage containing the same dose of WP and glucose.

STUDY DESIGN OVERVIEW

The study is a single-blind, randomised, acute, crossover intervention trial.

STUDY DESIGN

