Participants will complete four acute interventions (two pairs, as shown in Table 2 below) in a random order with at least a one week washout between studies (four study visits in total, each visit will last 2.5 hours). At each visit, participants will consume one of the four test beverages detailed in Table 2.

Table 2 Details of the four acute interventions provided to participants (one per study visit; four study visits in total)

[figure not shown]
| | | |
|------------------------|----------------|---|
| Pair 1 (WP vs FP) | Intervention 1 | Whey protein, WP; 0.4g/kg body weight |
| | Intervention 2 | Faba bean protein, FP; 0.4g/kg body weight |
| Pair 2 (WPG vs FPG) | Intervention 3 | Whey protein and glucose load, WPG; 0.4g/kg body weight WP + 50g glucose |
| | Intervention 4 | Faba bean protein and glucose load, FPG; 0.4g/kg body weight FP + 50g glucose |

An overview of the study assessments and the participant's journey through the study is shown in Figure 1 and a detailed description of the methods is given below.

In brief, the study will require participants to attend the Northern Ireland Clinical Research Facility (NICRF) at the Belfast City Hospital U-floor on four occasions at least one week apart (Visits 1,2,3,4); each of these visits will last 2.5 hours and participants will consume a beverage consisting of one of the above interventions at each visit.

Figure 1: Overview of participant's journey throughout the study

Four interventions will be delivered in random order: intervention #1 - WP; intervention #2 - FP; intervention #3 – WPG; intervention #4 – FPG.

PARTICIPANTS

A total of 20 healthy participants will be recruited (see sample size section for details). The specific inclusion and exclusion criteria are as follows:

Inclusion criteria

- 18-40 years old
- Healthy volunteers
- Body mass index (BMI) $\geq 18.5 \text{ kg/m}^2$ and/or weight $\geq 50\text{kg}$ (7 Stone 12 pounds) [minimum weight in line with NI Blood transfusion requirements]
- Be willing to consume WP and FP beverages
- Be available to meet the requirements of the study

Exclusion criteria

- Medical condition or medication known to affect glucose regulation or appetite and/or digestion and absorption of nutrients
- Known history of diabetes mellitus or the use of antihyperglycemic drugs or insulin to treat diabetes and related conditions
- Use of steroids, protease inhibitors or antipsychotics

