Compared to a 50g glucose control, Thondre et al. showed that there was a dose response effect of pea protein (25g and 50g) on postprandial glycaemia and stimulated insulin release over a three hour period in healthy adults (14).

RANDOMISATION AND BLINDING

The study will be a four-visit, single-blind, acute crossover study; with at least a one week washout period between visits. A computer-generated randomisation scheme will be prepared by a statistician who is independent of the study team and provided to the researcher who is preparing the test beverages (CK).

The researcher will prepare beverages for each visit for each participant according to the randomisation list. To maintain participant blinding, beverages will be provided in identical opaque containers labelled with the participant number and the intervention period. Thus, the participants will be unaware which beverage they are taking during each visit.

PROPOSED OUTCOMES

Primary endpoint: Circulating concentrations of intact GLP-1 in blood.

Secondary endpoints: Circulating concentrations of other satiety hormones, glucose and insulin concentration, amino acid availability in blood.

Exploratory endpoints: Metabolomic and proteomic markers in blood.

SAMPLE SIZE

Based on variability data from previously published studies in similar populations (6, 8), as well as unpublished data from our own group, a sample size of 16 participants will give the study 80% power to detect a significant difference of 10-15% in total AUC GLP-1 between treatment conditions (WP vs FB; or WPG vs FPG) or a difference in AUC Glucose of 5-15% between treatment conditions (WPG vs FPG).

To allow for dropout, it is anticipated that 20 participants will be recruited.

STUDY ASSESSMENTS

All assessments will be carried out at the Northern Ireland Clinical Research Facility, U Floor, Belfast City Hospital tower block.

Questionnaires (paper copies provided for completion):

All participants will be asked to complete a short lifestyle questionnaire (sex, age, food and drinks, alcohol, physical activity and smoking status (adapted from Leeds Short Form Food Frequency Questionnaire (20)); see Appendix 8.0) at their first visit.

Visual analogue scales (see Appendix 9.0) to rate feelings of hunger will be completed during each study visit at T0 (before the drink is consumed), T30, T60, T90 and T120 (minutes).

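### The stated ANOVA/Friedman and post hoc plan is not tied to the two contrasts the trial is sized for (FP−WP, FPG−WPG), and no protein-by-glucose term is pre-specified although the 2x2 design supports one

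*Protocol*

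**What the plan says.** All references are to the Protocol.

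- **Design.** Study Design states "Participants will complete four acute interventions (two pairs, as shown in Table 2 below) in a random order". The Figure 1 text lists the beverages: "Four interventions will be delivered in random order: intervention #1 - WP; intervention #2 - FP; intervention #3 – WPG; intervention #4 – FPG". Two protein sources crossed with glucose absent or present make a complete 2x2 within each person.
- **Aim and hypotheses.** The Aim is to "assess the acute effect of FP vs WP, with and without a glucose load". Question 1 compares FP with WP, and Question 2 compares them with glucose added to both. Hypothesis 2 reads "A beverage containing FP and glucose will attenuate the postprandial glycaemic response to a greater extent than a beverage containing the same dose of WP", again with glucose. Both are simple effects.
- **Sample size.** "a sample size of 16 participants will give the study 80% power to detect a significant difference of 10-15% in total AUC GLP-1", for differences "between treatment conditions (WP vs FB; or WPG vs FPG", or for "a difference in AUC Glucose of 5-15% between treatment conditions (WPG vs FPG". The sizing is per pair.
- **Analysis.** Statistical Analysis plans repeated measures ANOVA for normally distributed data and Friedman otherwise, comparing concentrations at each time point, with iAUC also calculated. Post hoc work is Bonferroni-corrected for parametric data and Wilcoxon signed-rank for non-parametric data, with significance at 0.05. The ANOVA factors, the set of comparisons Bonferroni covers and a protein-by-glucose term are not stated.

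**The concern.** The questions and sample size are built on two contrasts, while the analysis section is built on omnibus tests followed by unspecified post hoc comparisons. Two things follow.

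First, the usual reading of a four-level repeated measures ANOVA with Bonferroni post hoc tests is correction over all six beverage pairs. Four of those six cross the pairs (for example WP against FPG) and answer no question in the Protocol. They would take power from the two that do.

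Second, the same protein contrast will be reported twice, with and without glucose, with nothing planned to compare the two results. If one reaches significance and the other does not, the natural but unsound reading is that glucose changes the effect. An interaction estimate with its interval guards against that. A suitable ANOVA could supply one, but Friedman and Wilcoxon tests as described do not. Because the Protocol chooses the route by a Shapiro–Wilk test, whether an interaction is available at all could turn on a normality result.

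**Working it through.** **Inputs.** From Sample Size: 16 completers, 80% power, 10–15% difference in total AUC GLP-1 (5–15% for AUC glucose), 20 recruited. From Statistical Analysis: significance level 0.05, taken as two-sided because the side is not stated. The SD is not printed; the source is given only as "Based on variability data from previously published studies in similar populations (6, 8), as well as unpublished data from our own group". It is therefore back-solved. The correlation ρ between a person's two pair differences is not given either, and is varied.

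**1. The plan's own figure.** Without an SD, 16 cannot be reproduced, only inverted. For a paired t test with 15 df, 80% power at n = 16 needs a standardised paired difference dz = 0.749 (0.700 by normal approximation). The noncentrality is 0.749 × √16 = 3.00. The implied SD of a pair difference is 10/0.749 = 13.3% to 15/0.749 = 20.0%. Recruitment agrees with 20% dropout: 16/0.8 = 20.

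**2. Power of one planned contrast under different corrections.** Power = P(T > t_crit), with T noncentral t, noncentrality 3.00. Paired error has 15 df. Pooled error from one four-beverage model has 3 × 15 − 3 (periods) = 42 df and assumes equal variances.

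| Correction | Two-sided level | t_crit, 15 df | Power | t_crit, 42 df | Power |
|---|---|---|---|---|---|
| None | 0.05 | 2.131 | 80% | 2.018 | 83% |
| Two planned contrasts | 0.05/2 = 0.025 | 2.490 | 69% | 2.325 | 75% |
| All six pairs | 0.05/6 = 0.0083 | 3.036 | 51% | 2.769 | 59% |

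Moving from six comparisons to two recovers 69 − 51 = 18 points with paired error, or 75 − 59 = 16 with pooled error. Pooling alone, with no correction, adds about 3.

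**3. Interaction, (FPG−WPG) − (FP−WP).** Its SD is SD_d × √(2(1−ρ)), where SD_d is the SD of one pair difference. For an interaction as large as the planned pair effect, the standardised value is 0.749/√2 = 0.530 at ρ = 0 and 0.749 at ρ = 0.5. Power is 51% at ρ = 0, 63% at ρ = 0.25 and 80% at ρ = 0.5. At ρ = 0, 80% power would need 30 completers.

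**4. Protein effect averaged over glucose.** Its SD is SD_d × √((1+ρ)/2). At ρ = 0 the standardised value is 0.749 × √2 = 1.06. Power is 98% at ρ = 0, 94% at 0.25 and 90% at 0.5.

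**5. Chance that exactly one pair is significant.** With the same true effect in both pairs at 80% power and ρ = 0: 2 × 0.8 × 0.2 = 32%. By simulation it is 28% at ρ = 0.25 and 23% at ρ = 0.5. With no true difference in either pair and ρ = 0: 2 × 0.05 × 0.95 = 9.5%.

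**The case against.** The strongest reply is that nothing stated is left untested. The Protocol resolves the with-and-without-glucose aim into two questions, each with its own contrast, and Table 2 and the sample size match. No hypothesis asks whether glucose modifies the FP−WP difference, so the absence of an interaction term contradicts nothing. Model factors and the comparison family are often left to an SAP, and none is at hand here. The six-pair correction is one reading of an unspecified plan.

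Most of this stands, and it rules out several stronger readings a reader might infer:

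- **That the trial cannot test whether glucose changes the protein effect.** It can. Each completer supplies the difference of differences, and only the pre-specification is missing.
- **That part of the aim gets no test.** Each glucose condition has its own contrast.
- **That the pairs are analysed in separate models.** This holds for the questions, Table 2 and the sample size. The ANOVA could include all four beverages, and the text does not say.
- **That large precision is available for nothing.** The 98% belongs to an averaged effect, which neither hypothesis concerns, and requires ρ = 0. For the hypothesised contrasts, pooling takes 80% to 83% only without correction; with two contrasts corrected it is 75%.
- **That there is a 32% risk of a false glucose claim.** That figure needs equal true effects, 80% power in both pairs and ρ = 0, and the Protocol plans no such inference.

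What the reply does not remove is that the Protocol does commit to methods. Those methods neither name the contrasts the trial was sized for nor, on the non-parametric route, offer any comparison of the pairs.

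**Conclusion.** The point holds as one of analysis choice and pre-specification. The stated methods are a looser fit to the two planned contrasts than the design allows. The loss is conditional: if Bonferroni is applied to all six pairs, a contrast planned at 80% has about 51% power (paired error) or 59% (pooled error), against about 69% or 75% when only the two planned contrasts are corrected for. These figures rest on 16 completers, a two-sided 0.05 level and the back-solved dz of 0.749; the pooled figures also need similar variances with and without glucose.

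The interaction deserves a pre-specified estimate, but only a supportive one, with 51% power at ρ = 0 and 80% at ρ = 0.5 for an interaction as large as the pair effect. The averaged protein effect is a different estimand, hard to interpret if glucose modifies the effect, and at most supportive too. Neither ρ nor the SD is in the Protocol.

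**What to change.** Amend Statistical Analysis as follows.

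- For the AUC outcomes, fit one mixed model to all four beverages, with protein, glucose, protein-by-glucose, period and the T0 value as fixed effects and participant as a random effect.
- Name FP−WP and FPG−WPG, estimated from this model with 95% CIs, as the main results. Limit any multiplicity correction to these two.
- Report the interaction estimate with its 95% CI as supportive, and state that the two pair results will not be compared by whether each is significant. If the averaged protein effect is reported, label it supportive.

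This is a change of wording, with no extra participants, visits or samples. The one statistical cost is that pooled error assumes similar variance with and without glucose. Condition-specific variances, or paired contrasts at 15 df, relax that assumption at the price of the small pooling gain.

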There are a wide variety of plant-protein sources, such as legumes, pea, beans, oat, and soya protein and the EAA and non-EAA content differs according to the source (see examples in Table 1). As the popularity and demand for plant-based proteins grows, there has been an increase in the variety of commercially available sources. Many studies to date have focused on the functional and bioactive properties of soy protein compared to animal protein sources (15), whereas there is still limited knowledge of the physiological effects of other plant proteins such as pea and bean protein sources. Faba beans are emerging as sustainable and versatile plant protein source. Faba beans, also known as broad beans, have been grown across the UK for thousands of years. Approximately three quarters of a million tonnes of faba beans are harvested around the UK each year, with the majority being exported to the Middle East or used as animal feed. There is increased interest in faba bean as a potentially valuable crop to grow in Ireland. The 'Unlocking Protein Resource Opportunities To Evolve Ireland's Nutrition' (U-Protein) project aims to create new scientific and technological knowledge with long-term potential to re-engineer Ireland's agro-ecological system. It proposes to achieve this through greater diversification of protein resources, including faba bean, delivering sustainability, circularity and quality nutrition. As part of the U-Protein project, we aim to evaluate human metabolic responses to the consumption of faba bean protein (FP) sources which can be grown in Ireland.

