- Major medical or surgical event requiring hospitalisation within the preceding three months
- Any known food allergy or intolerance including lactose intolerance or milk allergy
- Pregnancy or lactating

- Donated blood to the NI Blood Transfusion Service in the last 12 weeks for men or 16 weeks for women

Eligible participants will be asked to fast from 21:00h (9pm) the night before and refrain from intensive physical activity for 24 hours prior to study visit. Intensive physical activity is defined as an activity that makes someone breathe hard and fast so it would be difficult to say more than a few words without pausing for breath, for example running, football, rugby, netball, hockey, aerobics, martial arts. Eligibility to participate in the study will be assessed using a screening questionnaire (Appendix 1.0) taking into consideration the above inclusion and exclusion criteria.

RECRUITMENT

Participants will be recruited from the student and staff population at Queen's University Belfast (QUB).

Students and staff will be made aware of the study in a number of different ways:

1. Poster advertisement (see Appendix 2.0)

With relevant permissions, an A4 poster will be placed around buildings frequented by staff and students from QUB, for example, the Medical Biology Centre (MBC), the School of Biological Sciences building, and the main site tower. The poster will include contact details so participants can contact the study team if interested to discuss the study further.

2. E-mail (see Appendix 3.0)

With permission from the relevant Head of School or Centre Director, an email will be sent to students enrolled for the 2023-2024 academic year within the School of Biological Sciences and the Centre for Biomedical Sciences Education, School of Medicine, Dentistry & Biomedical Sciences.

3. QUB Staff round-up (see Appendix 4.0)

Information about the study will be included in the QUB staff round-up.

4. Social Media (see Appendix 5.0)

With permission from the relevant gatekeeper, a post will be shared on the social media accounts of the Centre of Public Health and the Institute of Global Food Security and other relevant QUB social media streams.

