The main ethical considerations specific to the study protocol are in relation to the consumption of the study beverages and collection of blood samples at each study visit.

In relation to the study beverages, the WP and FB are both commercially available in the UK. The brand purchased will be Pulsin (www.pulsin.co.uk) which is produced to high safety and quality standards and is stocked by many of the UK main supermarkets and other major retailers. It is very unlikely that a participant would experience any undesirable effects from consuming these protein drinks, however, we will ask participants to rate the palatability of the beverages and will make it clear to participants that they can withdraw from the study at any time should they not wish to continue.

In relation to the blood samples, in total 60mls will be collected over a 2.5 hour period at each visit. If a participant completes all 4 visits, that means providing 240mls in total over a minimum of a one month period. This is well below the volume of blood collected during an NHS blood donation (450ml). As multiple blood samples will be collected at each visit, a trained phlebotomist at the NI Clinical Research Facility will insert a cannula at the start of each visit which will make collection of samples thereafter painless. Participants will be informed about the risk of minor discomfort and bruising associated with the insertion of the cannula and collection of blood.

Participants will present for each study visit in the morning after an overnight fast. They will consume the protein beverage during their visit, and we will also provide them with a cereal bar and a carton of juice at the end of the visit to ensure they are not excessively hungry before they leave.

CONFIDENTIALITY AND DATA STORAGE

The study participant information sheet describes how we will look after the data provided by participants and signposts to the QUB research privacy notice for research participants - www.qub.ac.uk/privacynotice/Research/ListofResearchPrivacyNotices/PrivacyNoticeforResearchParticipants

We will ensure that participant confidentiality is maintained throughout the study. When a participant consents to join the trial, they will be allocated a unique participant study ID which will be used to pseudonymise sensitive personal data collected during study visits with the key held by the research team in a password protected file.

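### The exclusion criteria do not cover G6PD deficiency or favism, although every participant is due two faba bean protein drinks

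*Protocol*

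**What the plan says.** The Background of the protocol identifies the test food plainly: "Faba beans, also known as broad beans, have been grown across the UK for thousands of years". Table 2 lists the faba arm without glucose as "Faba bean protein, FP; 0.4g/kg body weight", and a second faba drink combines the same protein dose with 50 g glucose. The design is a four-period crossover, so each participant is due both.

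Under Participants, three criteria could bear on a hazard of the test food:

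- the inclusion criterion "Healthy volunteers", which is not defined further;
- the exclusion criterion "Medical condition or medication known to affect glucose regulation or appetite and/or digestion and absorption of nutrients";
- the exclusion criterion "Any known food allergy or intolerance including lactose intolerance or milk allergy".

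The other exclusions concern diabetes and its treatment, certain drug classes, recent hospitalisation, pregnancy or lactation, and recent blood donation. On how the criteria are applied, the same section says: "Eligibility to participate in the study will be assessed using a screening questionnaire (Appendix 1.0) taking into consideration the above inclusion and exclusion criteria". No laboratory screening test is described.

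Ethical Considerations treats drinking the beverages as one of the two main ethical issues. It concludes: "It is very unlikely that a participant would experience any undesirable effects from consuming these protein drinks". The support offered is that both powders are on general sale and that the brand is made to high standards. The Background adds only that faba beans are free of common allergens. G6PD deficiency, favism and haemolysis are mentioned nowhere in the protocol.

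**The concern.** The criteria name hazards of the comparator (milk allergy and lactose intolerance) but not the recognised hazard of the test food. Favism is general medical knowledge about faba beans and does not depend on any one cited study. Because the gap lies in the eligibility criteria and the risk description, a statistical analysis plan would not be expected to fill it.

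What is at stake is participant safety and disclosure. The volunteers are healthy and expect no benefit. If the criteria are applied exactly as written, a person who knows that they have G6PD deficiency, but has never reacted to broad beans, can be enrolled and given two concentrated faba bean drinks. The primary endpoint, the sample size and the analysis are not affected.

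**Working it through.** The protocol has no figure of its own to reproduce on this point. The check is a reading of the criteria against four kinds of volunteer, followed by the exposure and a note on size.

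**Who is caught by the listed criteria**

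| Volunteer | Allergy/intolerance criterion | Medical-condition criterion | Healthy-volunteer criterion |
|---|---|---|---|
| Knows that they react to broad beans | Probably excluded; the dairy items are examples, not limits | Not covered | Uncertain |
| Known G6PD deficiency, no past reaction | Not covered; nothing to report as an allergy or intolerance | Not covered; a red-cell enzyme deficiency is not a condition of glucose regulation, appetite, digestion or absorption | Can be met by a person without symptoms, because the term is undefined |
| Family history of deficiency or favism only | Not covered | Not covered | Met |
| Undiagnosed, no family history | Not covered | Not covered | Met |

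The gap is therefore clearest in the second and third rows. The fourth row cannot be reached by any questionnaire.

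**Exposure**

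Table 2 gives 2 faba drinks among 4. At 0.4 g/kg, the protein per drink is 0.4 × 55 = 22 g at 55 kg and 0.4 × 90 = 36 g at 90 kg, which agrees with the range in the Dosage section.

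**Risk statement set against the hazard**

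General sale, brand quality and freedom from common allergens describe the product. Favism depends on the enzyme status of the person who drinks it. None of the reasons given addresses that.

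**Size**

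The protocol gives neither the prevalence of deficiency among likely recruits nor the vicine and convicine content of the powder, so the risk of harm per drink cannot be calculated. One limited illustration is possible. If a proportion p of recruits were deficient (an assumption), the chance of enrolling at least one among the planned 20 is 1 − (1 − p)^20:

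| Assumed p | Chance of at least one among 20 |
|---|---|
| 0.1% | 2.0% |
| 0.5% | 9.5% |
| 1% | 18.2% |
| 2% | 33.2% |
| 5% | 64.2% |

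This is the chance of enrolment with no screening for the deficiency. It counts diagnosed and undiagnosed people together, and it says nothing about whether any of them would be harmed.

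**The case against.** The strongest reply is that the protocol contradicts nothing in itself. The hazard is brought in from general knowledge, and whether this processed powder carries it is unknown. That limits what can be said about size. It does not remove the point, because the hazard is an established property of the food under test, and following the criteria exactly could expose a susceptible person.

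Second, existing safeguards count for something. The food criterion is a catch-all that probably covers known reactors. The participant-facing short title names broad bean, volunteers must be willing to take the drinks, and they have at least 48 hours and the chance to ask questions. A well-informed volunteer with a known deficiency might withdraw unprompted. This narrows the gap but leaves it to the volunteer to make the connection.

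Third, a reader might infer that nobody asks about G6PD deficiency. The documents do not support that. The screening questionnaire (Appendix 1.0) and the information sheet (Appendix 6.0) are not shown. The questionnaire takes the listed criteria into account but is not said to be confined to them. What can be said is that the criteria do not require the question.

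Fourth, a reader might expect haemolysis to disturb the metabolomic and proteomic samples. Nothing in the protocol shows this: sampling ends at 120 minutes, visits are at least a week apart, and those endpoints are exploratory.

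Fifth, the statement that undesirable effects are very unlikely is not shown to be wrong, since a rare susceptibility is compatible with it. The fault is that it leaves the susceptibility out.

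**Conclusion.** The point holds as a gap in the listed criteria and in the risk description. As written, the criteria do not exclude a volunteer with known G6PD deficiency, or a first-degree family history of G6PD deficiency or favism, who has never reacted to broad beans. Each participant is due two faba bean drinks.

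The conclusion rests on one piece of general medical knowledge (faba beans can cause haemolysis in G6PD-deficient people) and on reading intolerance in its ordinary sense. The risk per drink is unknown and may be low. The enrolment percentages depend on assumed prevalences, and it would be a mistake to read them as a risk of harm. They also overstate what screening questions could prevent, since they include undiagnosed people.

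This should be fixed, preferably before enrolment. It is not graded higher because the hazard of this particular powder is undocumented, the catch-all probably covers known reactors, and the two unseen appendices may already deal with the matter.

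**What to change.** 1. Add to the exclusion criteria known G6PD deficiency, or a personal or first-degree family history of G6PD deficiency or favism.
2. Check that the screening questionnaire (Appendix 1.0) asks about this, and add an item if it does not.
3. Qualify the risk sentence under Ethical Considerations so that it mentions the susceptibility, and bring the information sheet (Appendix 6.0) into line.

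The study team and the ethics committee should settle the final wording.

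The cost is one criterion, one or two questionnaire items and a sentence in each of two places. No laboratory test is needed, and no visit, sample size or analysis changes. There are two downsides: an occasional volunteer is turned away, and undiagnosed people without a family history are still not detected.
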